### **3. Methods**

#### **Study design**

Single centre, open-label, single group pilot study with a follow up of 12 months.

#### **Sample size**

A prospective study (15) demonstrated a re-intervention free rate of 55% at 12 months for balloon dilatation. Assuming the re-intervention free survival rate at 12 months would be 55% for balloon dilatation (Group B) vs 15% for short term stenting with a biodegradable stent (Group A) yielded a sample size of  $n = 21$  per group. Allowing for a drop out rate of 15%, rendered a total sample size of 50 to attain a power of 80% and a 2-sided alpha level of 0.05. An interim analysis is planned when 50% of the intended total number of study subjects had passed their 3-month visit. We aim to enroll 21 prospective patients into Group A and use a historical cohort for Group B (undergone balloon dilatation in the last 5 years at King's College Hospital). A sample size of 21 was calculated (confidence 0.90, probability 0.1).

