duct dilatation on imaging. Patients who develop high grade, clinically relevant strictures have an increased risk of cholangiocarcinoma, which can occur in up to 26% of patients with significantly reduced overall survival compared to those without high grade strictures (7). High grade strictures should be interrogated via ERC to investigate for the presence of a malignant stricture with tissue obtained via brushings for cytology and consideration of cholangioscopy and biopsy, which has higher sensitivity with comparable specificity (6, 8, 9).

In patients undergoing stenting in PSC, plastic stents are the primary intervention. These small-diameter stents can develop biofilms and occlude over time, possibly leading to cholangitis (10). Biodegradable stents are increasingly being used in a variety of indications (11, 12). They are a novel alternative that may confer benefit in the reduction of treatment-related adverse events by removing the necessity of repeat procedures for stent removal. They are made of polydioxanone (a synthetic biodegradable polymer). These stents have been clinically effective and safe in patients with symptomatic biliary obstruction (12, 13). They hydrolyse with variable degradation times. Similar to plastic stents, they have an introducer that allows placement over the target area, and positioning can be visualised fluoroscopically. The Archimedes stent is a commercially available biodegradable stent produced by AMG International (14). Clinical utilisation of these stents demonstrating excellent safety and efficacy are now emerging (12, 13).

In patients with PSC, endoscopic therapy of strictures aims to improve cholestasis by relieving the biliary obstruction via endoscopic biliary dilatation with consideration of plastic stents in strictures refractory to dilatation due to the risk of pancreatitis and cholangitis (15-17). Short term stents have been shown to have similar recurrence-free

rates compared to dilatation in a randomised control trial; however, this was terminated after interim analysis due to higher rates of serious adverse events in the stent group (15). The long term benefits are unclear; however, it may lead to improved survival compared to predicted survival (18). In this group of patients with limited treatment options, biodegradable stents may provide an attractive additional treatment modality in the management of high grade strictures.

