## **2. AIMS**

### **Research hypothesis**

The use of biodegradable stents leads to remodelling of high grade strictures in patients with PSC with fewer interventions in comparison to balloon dilation alone with a comparable risk profile to current therapy.

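### The sample-size calculation assumes the stent is 40 points worse than balloon dilatation (15% vs 55% re-intervention-free), opposite to the hypothesis, so the stated 80% power is not tied to any stent benefit the protocol defines

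*Protocol*

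**What the plan says.** The research hypothesis (Protocol, section 2) is that biodegradable stents remodel high grade strictures "with fewer interventions in comparison to balloon dilation alone", so the stent is expected to do better.

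The Sample size section (Protocol, section 3) opens with the control rate from the literature: "A prospective study (15) demonstrated a re-intervention free rate of 55% at 12 months for balloon dilatation". It then states the planning assumption: "Assuming the re-intervention free survival rate at 12 months would be 55% for balloon dilatation (Group B) vs 15% for short term stenting", where the second figure belongs to the study stent, labelled Group A. From this it derives 21 per group. Dropout is then added: "Allowing for a drop out rate of 15%, rendered a total sample size of 50". The targets given for this total are 80% power and a two-sided alpha of 0.05.

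The same section plans 21 prospective patients in Group A and takes Group B from patients treated at the centre in the last five years. It gives no final size for Group B. It closes with a second, very short basis for 21: confidence 0.90 and probability 0.1. The primary endpoint is technical success and safety of stent placement, and the design is a single-group pilot.

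**The concern.** Taken literally, 45% of balloon patients and 85% of stent patients would need re-intervention within 12 months. A calculation on those rates is sized to show harm from the stent, not benefit. Nothing in the protocol explains the reversal, and nowhere does it give a stent rate above 55%.

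This would matter less if the two rates stood beside a calculation made on other inputs. They do not: the stated 21 and 80% come from them. The protocol therefore attaches 80% power to a comparison without naming a benefit for which that power holds. A reader of a non-significant result could take it as coming from an adequately powered comparison when it did not.

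**Working it through.** **Inputs.** From the Sample size section: 55% (balloon), 15% (stent), two-sided alpha 0.05, power 80%, 21 per group, 15% dropout, total 50. Equal group sizes are implied by the per-group figure. The 85%, 45% and 95% free rates used below are readings of the text or assumptions, not protocol figures.

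**Formulas** (pooled normal approximation, p̄ = mean of the two rates when groups are equal):

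- n per group = [1.960·√(2p̄(1−p̄)) + 0.842·√(p₁(1−p₁) + p₂(1−p₂))]² / (p₁−p₂)²
- Power = Φ{(|p₁−p₂| − 1.960·SE₀) / SE₁}, where SE₀ uses the pooled rate and SE₁ the separate rates

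**1. The plan's own figures, 55% vs 15%.** p̄ = 0.35.

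- n = (1.3221 + 0.5154)² / 0.16 = 21.1 per group. The arcsine formula gives 20.5, which rounds up to 21.
- Power at 21 per group = Φ{(0.40 − 1.960 × 0.1472) / 0.1336} = Φ(0.834) = 79.8%.
- Dropout: 42 / 0.85 = 49.4, so 50.

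All three stated figures reproduce.

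**2. Readings that would favour the stent.**

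| Reading (balloon vs stent, % free) | n per group for 80% | Power at 21 per group | Agrees with the cited 55% free? |
|---|---|---|---|
| Arm labels swapped: 15 vs 55 | 21.1 | 79.8% | No |
| Both figures are re-intervention rates: 45 vs 85 | 21.1 | 79.8% | No |
| Only the 15% is a re-intervention rate: 55 vs 85 | 35.4, so 36 | 56.8% | Yes |
| Same 40-point gap, reversed: 55 vs 95 | 17.2, so 18 | 87.8% | Yes, but 95% appears nowhere |

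For the third row, p̄ = 0.70: n = (1.2702 + 0.5154)² / 0.09 = 35.4, and power = Φ{(0.30 − 1.960 × 0.1414) / 0.1336} = Φ(0.171) = 56.8%. Other methods for that row give 59% (arcsine), 61% (unpooled) and 45% (Fisher's exact test).

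So the two readings that reproduce 21 contradict the cited balloon rate, and the two that keep the cited rate do not reproduce 21.

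**3. How far the power depends on the unknowns.**

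- Stent rate, against 55% with 21 per group: 70% free gives 17%, 75% gives 27%, 80% gives 41%, 85% gives 57%, 90% gives 74%, 95% gives 88%. Power reaches 80% at a stent rate of about 92%.
- Size of Group B, for 85% vs 55% with 21 stent patients: 21 controls give 57%, 40 give 67%, 60 give 72%, 100 give 77%.
- Dropout: Group A is planned at 21 with no allowance for the 15%. 0.85 × 21 = 17.85, about 18. With 18 evaluable in each group (assumed), power for 85% vs 55% is 50%.

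**The case against.** **The 57% rests on an inference.** A reader might conclude that the trial simply has 57% power instead of 80%. The document does not support that. The 85% is the complement of 15%, not a protocol figure, and the result also needs exactly 21 controls, which the enrolment sentence does not fix. This objection stands, so the 57% can be given only with its conditions.

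**A reading that keeps 21 exists.** If the word free was misapplied to both figures, 45% vs 85% free has the right direction and 79.8% power. It cannot be excluded without the cited trial. But it moves the error to the preceding sentence, which reports the 55% as "demonstrated a re-intervention free rate of 55% at 12 months for balloon dilatation". Something in the section is wrong on either reading.

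**Group A may not depend on this calculation.** The closing sentence gives another basis for 21. If it means the chance of seeing at least once an event of 10% frequency (an assumption, as the protocol does not say), then ln(0.1)/ln(0.9) = 21.9, and 21 patients give 1 − 0.9²¹ = 89%. That would suit a pilot with a safety endpoint. This stands and limits the consequence: the enrolment of 21 may be defensible, although the 80% power statement is not rescued by it.

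**The comparison is not the primary endpoint** and is not randomised. This is true and lowers the stakes, but the protocol still states a power for it.

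**The Background does not rule out a large benefit.** The sentence beginning "Short term stents have been shown to have similar recurrence-free" might be read as showing that a 40-point gap is implausible. It concerns short-term stents in an earlier randomised trial, while the protocol presents biodegradable stents as a novel alternative. It offers no support for a large benefit, but it does not bound one either.

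**Conclusion.** The contradiction is certain on the text: the assumed rates put the stent 40 points below balloon dilatation, against the stated hypothesis, and those rates generate the 21 per group and the 80% power. The figures given contain no reading that keeps the cited 55% balloon rate, favours the stent and yields 21.

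The resulting loss of power is conditional. With 85% vs 55% free, about 36 per group are needed, and 21 per group gives about 57%, assuming 21 controls, complete follow-up and the pooled normal approximation. With 45% vs 85% free there is no loss, but the cited control rate has to be corrected. What the power really is cannot be settled from this document. The point calls for a correction before the 80% is relied on. It is not evidence that 21 patients are too few for the pilot's primary endpoint.

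**What to change.** Either of two changes to the Sample size section would do.

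1. **Keep a powered comparison.** Check the cited 12-month rate in the source trial. Express both rates on one scale, re-intervention-free or re-intervened, with the stent as the better arm, and justify the stent rate. State how many historical controls Group B will contain and how many Group A patients are expected to be evaluable after dropout. Then restate whatever power results.
2. **Make the historical comparison exploratory.** Remove the 80% power statement and the 55% vs 15% derivation. Rest the 21 on the basis already given at the end of the section, spelling out what confidence 0.90 and probability 0.1 refer to and how they relate to technical success and safety.

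The cost is protocol wording only. No extra patients are required by the correction itself, but under the first option the stated power may come out less favourable than 80%.

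### The 15% drop-out allowance is calculated but not applied to Group A, and Group B has no stated size, so the stated 80% power is not supported by the numbers given

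*Protocol*

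**What the plan says.** All of this is in the Sample size section of the protocol (section 3, Methods).

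- The assumed rates are given as "Assuming the re-intervention free survival rate at 12 months would be 55% for balloon dilatation (Group B") against "15% for short term stenting with a biodegradable stent (Group A"), which leads to 21 per group.
- The drop-out step follows: "Allowing for a drop out rate of 15%, rendered a total sample size of 50 to attain a power of 80" percent. The operating characteristics attached to it are "to attain a power of 80% and a 2-sided alpha level of 0.05".
- An interim analysis is set for when half of the intended total have passed the 3-month visit. The text does not say which total is meant.
- The enrolment plan is "We aim to enroll 21 prospective patients into Group A and use a historical cohort for Group B", the latter being patients who had balloon dilatation at the same hospital in the last 5 years. No number is given for that cohort.
- The paragraph closes with a second basis for 21: "A sample size of 21 was calculated (confidence 0.90, probability 0.1"). It names neither a formula nor the event concerned.

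The Study design section describes a single-group pilot with 12 months of follow-up. The primary endpoint is technical success and safety of stent placement.

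**The concern.** The paragraph treats 21 in two ways. In the power calculation it is the number each group must have after losses, which is why it is inflated to 25 per group. In the enrolment plan it is the number recruited before losses. Group A is the only group followed prospectively, so it is the one in which patients will be lost during the study, and it is the one that does not receive the allowance.

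A smaller Group A could be offset by a larger historical cohort, but the protocol fixes no size for Group B. A reader therefore cannot confirm the 80% from the document.

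The mismatch also affects an operational rule. The only total printed is 50, and half of it is 25. If the interim trigger counts prospective patients only, 25 can never be reached with 21 enrolled.

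**Working it through.** **Inputs (all from the Sample size section).** Group B 55%, Group A 15%, two-sided alpha 0.05, power 80%, drop-out 15%, Group A enrolment 21. The rates are taken as printed. The size of Group B is not given, so it is varied below.

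**Step 1: reproduce 21 per group.** The pooled normal formula gives 22 and the arcsine formula gives 20.5, so 21. Power for 21 against 21 by the pooled normal formula is

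Φ[(|p_B − p_A| − 1.96·SE0)/SE1],

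where SE0 = √[p̄(1−p̄)(1/n_A + 1/n_B)], SE1 = √[p_A(1−p_A)/n_A + p_B(1−p_B)/n_B], and p̄ is the size-weighted mean rate.

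With p̄ = 0.35, SE0 = 0.1472 and SE1 = 0.1336: (0.40 − 1.96 × 0.1472)/0.1336 = 0.834, and Φ(0.834) = 79.8%. The plan's 21 and 80% reproduce. Fisher's exact test gives only 69.6% at 21 against 21, so it is not the method behind the stated figure and is not used here.

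**Step 2: reproduce 50.** 2 × 21 = 42, and 42/0.85 = 49.4, so 50. Per group, 21/0.85 = 24.7, so 25. The total of 50 thus comes from equal groups of 25.

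**Step 3: apply the plan's drop-out to the planned enrolment.** 21 × 0.85 = 17.85, about 18 evaluable in Group A at 12 months.

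**Step 4: power with 18 in Group A, same formula.**

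| Evaluable in Group B | Power |
|---|---|
| 18 | 73.0% |
| 21 | 76.0% |
| 25 | 79.1% |
| 27 | 80.4% |
| 29 | 81.6% |
| 42 | 86.7% |

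Worked example for 18 against 21: p̄ = (18 × 0.15 + 21 × 0.55)/39 = 0.365, SE0 = 0.1547, SE1 = 0.1374, (0.40 − 1.96 × 0.1547)/0.1374 = 0.705, and Φ(0.705) = 76.0%. The smallest Group B that reaches 80% is 27.

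**Step 5: interim trigger.** Half of 50 is 25, which exceeds 21. Half of 21 is 10.5, so 11. If historical controls count, their 3-month visits are already past and the trigger has no clear timing.

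**The case against.** **The power may still be met.** Group B's size is open. If the total of 50 is kept with 21 in Group A, Group B would be 29, and 18 against 29 gives 81.6%. This stands in part: a reader might infer that the 80% is simply missed, and the document does not establish that. But the protocol nowhere describes a 21 + 29 split. It derives 50 from equal groups, and it commits to no Group B number that would compensate.

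**The shortfall is small and 18 may be pessimistic.** The baseline of 21 against 21 is itself 79.8%, so the loss with 21 controls is under 4 points, and with 25 controls it is negligible. The 73.0% for 18 against 18 applies the same loss to a retrospective cohort and is not the natural case. If re-intervention-free survival is analysed with censoring, patients lost would still contribute follow-up time. All of this stands and limits the size of the point.

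**The primary endpoint is hardly touched.** Technical success is assessed at the procedure, so 12-month drop-out matters little for it. That also stands. The power statement concerns a historical comparison on an outcome that is not the primary endpoint.

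**The second basis for 21.** A reader might infer that confidence 0.90 with probability 0.1 should give 22. If it means seeing at least one event of probability 0.1, then ln(0.1)/ln(0.9) = 21.85, and 21 patients give 1 − 0.9^21 = 89.1%. But the protocol names no formula, and the difference is one patient of rounding. It is not an error that can be charged to the plan.

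**Conclusion.** The inconsistency holds: the allowance for 15% loss is worked out correctly but not carried into Group A's enrolment, which leaves about 18 evaluable where the calculation needs 21. The stated 80% does not follow from the stated per-group number. Power is about 76% with 21 evaluable controls and about 79% with 25, and reaches 80% only from about 27.

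The conclusion is that 80% is unsupported as written, not that it is unattainable, because the size of Group B is left open. The figures assume the printed rates, a comparison of proportions by the pooled normal formula, 15% loss in Group A, and Group B sizes that are already net of any missing data.

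The interim trigger is ambiguous for the same reason. A reader might infer that it is based on 50, but the text does not say so.

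This should be corrected. It does not undermine the primary endpoint.

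**What to change.** Revise the Sample size paragraph so that it uses one consistent set of numbers:

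1. State 21 enrolled in Group A and about 18 evaluable at 12 months after 15% drop-out.
2. State that Group B will include all eligible patients from the 5-year window, and give that number. At least about 27 evaluable are needed for 80% with 18 in Group A.
3. Remove the equal-group total of 50 and the 80%, and quote the power for the actual numbers in both groups. Do not fix a range in advance, because it changes with the size of Group B.
4. State whether the interim trigger is counted on the 21 prospective patients (about 11 past the 3-month visit) or on another total.
5. If the second basis for 21 is kept, name its formula and the event it refers to.

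The cost is protocol wording and a count of the eligible historical patients, with no extra recruitment. The downside is that the stated power may become slightly less favourable if fewer than about 27 controls are available. The alternative is to enrol 25 in Group A, which leaves about 21 evaluable (25 × 0.85 = 21.25) and restores 79.8% against 21 controls, at the cost of four more patients.

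### The stated total of 50 and 80% power describe two equal recruited groups, but only Group A is recruited; Group B's size and selection rule should be stated and the power restated for the design actually planned

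*Protocol*

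**What the plan says.** All of this stands in the Sample size section of the protocol (section 3, Methods).

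- The control rate comes from a cited trial: "A prospective study (15) demonstrated a re-intervention free rate of 55% at 12 months for balloon dilatation".
- It is set against "vs 15% for short term stenting with a biodegradable stent (Group A"), giving 21 per group.
- The total is then inflated: "Allowing for a drop out rate of 15%, rendered a total sample size of 50 to attain a power of 80" per cent, with "a 2-sided alpha level of 0.05".
- The operative sentence follows: "We aim to enroll 21 prospective patients into Group A and use a historical cohort for Group B". Group B consists of patients treated with balloon dilatation over the past five years at the same hospital.

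The section gives no separate number, cap or selection rule for Group B, no count of available records and no balloon rate observed at the centre. It closes with a second derivation of 21, from a confidence of 0.90 and a probability of 0.1. Elsewhere, the Study design section calls the trial a single-group pilot, and the primary endpoint is technical success and safety.

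**The concern.** Equal groups and a drop-out allowance in both suit a trial that recruits both arms. Here only Group A has to be recruited and followed. Group B has already been treated, so its size is set by how many eligible records exist.

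Two things follow. First, the allowance sits in the wrong place: the total of 50 contains a margin for a group that cannot drop out prospectively, while the group that can is enrolled at 21 with no margin. Second, the stated power belongs to a design that will not be run, and nothing in the protocol says whether Group B will be 21, 25 or every eligible record. If more records exist, using them would sharpen the comparison without recruiting anyone. If the choice stays open, a subset could be picked after Group A results are known.

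**Working it through.** **Inputs.** Re-intervention-free rate at 12 months: Group B 0.55 and Group A 0.15; two-sided alpha 0.05; power 80%; 21 per group; drop-out 15% (all from the Sample size section). The number of historical records is not given, so 42 and 63 (two and three times 21) are an assumed range.

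**Step 1: reproduce the plan.**
- The arcsine formula gives 20.5, so 21 per group. The pooled-variance formula gives 22. The stated 21 reproduces.
- Drop-out: 21/0.85 = 24.7, so 25 per group and 50 in total. This also reproduces, and it shows that the allowance was applied to both groups.

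**Step 2: power for unequal groups.** With p̄ the size-weighted mean rate,

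s0 = √[p̄(1−p̄)(1/nA + 1/nB)], s1 = √[pA(1−pA)/nA + pB(1−pB)/nB], power = Φ[(|pA−pB| − 1.96·s0)/s1].

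- 21 vs 21: p̄ = 0.350, s0 = 0.1472, s1 = 0.1336; (0.40 − 0.2885)/0.1336 = 0.83; power 79.8%.
- 21 vs 42: p̄ = 0.417, s0 = 0.1318, s1 = 0.1094; (0.40 − 0.2583)/0.1094 = 1.30; power 90.2%.

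**Step 3: Group A after drop-out.** 21 × 0.85 = 17.85, about 18 evaluable. For 18 vs 21: p̄ = 0.365, s0 = 0.1547, s1 = 0.1374; (0.40 − 0.3032)/0.1374 = 0.70; power 76.0%.

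**Step 4: range of record counts.** The half-width is 1.96·s1, for Group A = 21.

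| Group B records | Power, A = 21 | Power, A = 18 | 95% half-width of difference, A = 21 |
|---|---|---|---|
| 21 | 79.8% | 76.0% | 26.2 points |
| 25 | 82.9% | 79.1% | 24.8 points |
| 42 (assumed) | 90.2% | 86.7% | 21.4 points |
| 63 (assumed) | 93.9% | 90.7% | 19.6 points |

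With 18 records and Group A at 21, power is 76.8%. However large Group B is, Group A alone leaves 1.96·√(0.15 × 0.85/21) = 15.3 points. Fisher's exact test is lower but moves the same way with Group A at 21: 69.6%, 78.2%, 87.9% and 93.1% for 21, 25, 42 and 63 records.

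**Step 5: dependence on the borrowed 55%.** With Group A at 15% and 21 vs 21, power is 56.8% if the centre's balloon rate is 45%, 69.1% at 50%, 88.3% at 60% and 94.1% at 65%.

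**The case against.** The strongest reply is that nothing is capped. A reader might infer that the protocol limits Group B to 21 or 25 records. It does not: those figures come only from the equal-group calculation, and "use a historical cohort for Group B (undergone balloon dilatation in the last 5 years") can already mean every eligible record. The selection rule may also be in a statistical analysis plan that is not at hand. This stands. What remains is that the protocol's own total and power sentence do not match the design described next to them.

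A reader might also infer that counting the centre's own balloon rate raises power. It does not. It replaces an untested planning value, and the restated power can fall (Step 5). Nor is that rate clearly the largest unknown, since the Group A rate is at least as uncertain. As printed, 15% re-intervention-free runs against the hypothesis of fewer interventions. If 15% was meant as a re-intervention rate (85% free, an assumption), power with Group A at 21 is 56.8%, 59.7%, 67.7% and 72.9% for 21, 25, 42 and 63 records. That is a separate matter, but the gain from more records has the same direction under either reading.

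Third, the benefit depends on a count that nobody has stated. Some entry criteria need graded symptom changes, and the documents do not say whether old charts hold them. This also stands.

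Finally, this is a pilot whose primary endpoint is technical success and safety, and the second derivation may be the working basis for enrolling 21. That lowers the weight of the point. It does not remove it, because the comparison with balloon dilation is the research hypothesis and carries the only power claim in the protocol.

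**Conclusion.** The point holds in a limited form. The figures of 21 per group and 50 in total are arithmetically sound for two recruited groups, but they do not describe a trial that enrols 21 patients and compares them with existing records. On the plan's own rates, 15% loss in Group A takes power to 76.0% (21 records) or 79.1% (25), slightly below the stated 80%.

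Using every eligible record could raise power to about 90% or more and narrow the half-width of the difference from 26 to about 20 points, but only if some 42 to 63 records exist, which is assumed. With 25 or fewer there is little or no gain. The benefit is sampling precision in a non-primary comparison, limited by Group A's size. It does not touch bias from selection or era. It is worth considering as a low-cost improvement and does not put the primary endpoint in question.

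**What to change.** In the Sample size section:

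1. State that Group B is all consecutive patients in the five-year window who meet the Group A eligibility criteria as far as the records allow.
2. Identify and lock that list before the first Group A patient is treated, or at the latest before any Group A outcome or the interim analysis is seen. Waiting until the first 12-month outcome would be too late in an open-label study with an interim tied to the 3-month visit.
3. Report the number of eligible records, how many have a complete 12-month outcome, and the observed re-intervention-free rate.
4. Replace the sentence on a total of 50 and 80% power with the power, or the expected confidence-interval width, for the evaluable Group A against that number. Apply any drop-out allowance to Group A only.

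The cost is additional chart review, of an extent that the documents do not allow one to estimate, and one rewritten paragraph. No extra patient is recruited. The sponsor should expect that the restated power may be less favourable than the present 80%.

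### The interim trigger, half of a stated total of 50, does not fit 21 prospective patients and a historical comparator, and should be restated in prospective patients

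*Protocol*

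**What the plan says.** All the relevant statements are in the protocol under 3. Methods, Sample size. A two-group calculation gives 21 per group, and after a 15% allowance for dropout it "rendered a total sample size of 50 to attain a power of 80% and a 2-sided alpha level of 0.05". The next sentence sets the interim: "An interim analysis is planned when 50% of the intended total number of study subjects had passed their 3-month visit". The section then describes a different structure: "We aim to enroll 21 prospective patients into Group A", with Group B taken from patients dilated at the same hospital over the previous five years. The Study design section calls the trial a single-group pilot.

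The protocol does not say whether historical patients count towards the trigger, how many there will be, or what the interim is for. The Primary endpoint section names technical success and safety of stent placement. The follow-up text names contacts on day 1, at week 2 and at week 52. Week 12 appears only in the liver-test endpoint. The flow chart is not shown, so a 3-month visit may be set out there.

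**The concern.** The trigger reads as if written for two groups followed side by side, where half of 50 would be 25 patients drawn from both arms. Here only one group is followed forward. A count of 25 either exceeds that group or is filled mostly by patients treated before the trial began.

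The interim matters because safety is half of the primary endpoint, and the Background reports that the earlier randomised trial of short-term stents was stopped early: "this was terminated after interim analysis due to higher rates of serious adverse events in the stent group". This interim is the only planned aggregate look before the end that the protocol describes. Applied with the stated total, it gives either no look at stent patients or a look at very few of them.

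**Working it through.** **Inputs, all from the Sample size section.** 12-month re-intervention-free rates of 0.55 and 0.15; power 80%; two-sided alpha 0.05; 21 per group; dropout 15%; total 50; 21 prospective patients; trigger at 50% of the total.

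**1. Where the 50 comes from.** Pooled two-proportion formula, no continuity correction:

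n = [1.96 × √(2 × 0.35 × 0.65) + 0.842 × √(0.55 × 0.45 + 0.15 × 0.85)]² / 0.40²
= [1.96 × 0.6745 + 0.842 × 0.6124]² / 0.16 ≈ 21.1, rounded up to 22 per group.

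The arcsine version gives 20.5, so 21. Power at 21 per group is 79.8%. The stated 21 is therefore reproduced.

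Dropout: 21 / 0.85 = 24.7, so 25 per group; 42 / 0.85 = 49.4, so 50 in total. The 50 is thus the dropout-inflated size of two groups. It comes from a fixed design at the full two-sided 0.05.

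**2. The trigger under each reading of the total.**

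| Total taken as | Half | Compared with 21 prospective patients |
|---|---|---|
| 50 (the only stated total) | 25 | 4 more than will be enrolled |
| 42 (2 × 21, before dropout) | 21 | every prospective patient, so hardly an interim |
| 21 (prospective patients only) | 10.5, so 11 | reachable |

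Enlarging Group A to the inflated 25 would not rescue the first row: the trigger would then need all 25 patients, with none lost.

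**3. If historical patients count towards 25.** The protocol gives no cohort size. Assume 21 to 25, the per-group figure before and after dropout, and assume nearly all are more than 3 months past dilatation. The second assumption is reasonable for a five-year window: with dilatations spread evenly, 3/60 = 5% would fall in the last 3 months. The stent patients then needed are 25 − 21 = 4 down to 25 − 25 = 0.

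**The case against.** **The trigger can be read so that it works.** The study is called single-group, 21 patients are enrolled, and historical patients have no study visits to pass. On that view the total is 21 and the trigger is 11. This stands as far as it goes: a reader might infer that the interim can never happen, and the documents do not support so strong a claim. But the protocol never calls 21 the total, and the interim sentence directly follows the one that states 50. The workable reading has to be supplied by the reader.

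**The type I error.** A reader might also infer that the interim inflates the error rate. Two unadjusted looks at 0.05, the first at half information, would give about 8.3% overall (about 9.1% to 8.0% for information fractions of 0.25 to 0.60). The documents do not establish this. No interim test or purpose is stated, a safety or feasibility look spends no efficacy alpha, and boundaries may properly sit in an analysis plan that is not shown. The 0.05 also belongs to the 12-month re-intervention comparison and not to the primary endpoint. Nor does half information match either problem reading. With prospective patients only, there is no look. With historical patients counted, 4 stent patients against 21 historical carry 1/(1/4 + 1/21) = 3.36, against 21/2 = 10.5 at full size, a fraction of 0.32; with no stent patients the fraction is zero. What stands is narrower: the sample size reserves nothing for a comparative look, should one be intended.

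**Patient safety.** Individual follow-up does not depend on the interim. The protocol provides a structured interview on day 1, a week-2 contact about complications, and access to the clinical team. This stands and limits the consequence.

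**Conclusion.** The point holds as an internal inconsistency. The stated total puts the trigger at 25, which is 4 more than the 21 patients to be followed prospectively. If historical patients fill the count, about 0 to 4 stent patients suffice, on the assumed cohort of 21 to 25 nearly all beyond 3 months. Only reading the total as the 21 enrolled gives a usable trigger, 11 patients, and the text does not say that.

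Leaving detail to an analysis plan does not cure this, because the protocol itself fixes the threshold and an analysis plan would have to override it. No type I error problem is shown. Since no decision rule is attached to the interim, the wrong count does not by itself damage the primary result. Severity: should-fix.

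**What to change.** Replace the interim sentence with wording such as: *An interim review takes place when 11 of the 21 prospective Group A patients have passed their 3-month (week 12) assessment. Historical patients do not count. The review covers technical success and safety, and no test against Group B is made.* This treats the 3-month visit as the week-12 assessment, which the sponsor should confirm against the flow chart.

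If a comparative test is intended, say so and account for its alpha. For two looks with the first at half information, O'Brien-Fleming boundaries would use two-sided levels of 0.0052 and then 0.0480.

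An earlier trigger at the week-2 contact is optional. If 21 patients enrol evenly over 12 months (assumption: the 24-month study less 12 months of follow-up), accrual is 21/12 = 1.75 per month and the 11th patient enters at 11/1.75 = 6.3 months. The 3-month trigger then falls at about month 9.3, with about 16 enrolled; a week-2 trigger falls at about month 6.8, with about 12 enrolled. Fewer patients would already have been treated, but the review would hold less week-12 data.

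The cost is a few sentences, with no change to enrolment or visits.
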